**Purpose**

The present study is designed to examine the effect of changes in body weight and related parameters associated with a commercially-available, low-carbohydrate diet plan. A parameter proposed to be studied here is to measure the impact of fructose restriction and weight loss on serum uric acid concentrations and arterial stiffness.

**Background**

It is well known that consumption of a calorically-restricted diet helps people lose weight. A calorie-restricted diet with low carbohydrate lowers the serum uric acid concentration which is a factor associated with obesity and also represents a particular metabolic risk in women compared to men. The present weight loss study will determine whether women benefit more than men to short-term weight loss occurring during restriction of simple sugars.

Recent epidemiologic data in humans have identified hyperuricemia as a risk factor for cardiovascular (CV)-related disease in women, raising the risk of coronary heart disease by approximately 70% compared to its effect in men (1). Two studies focusing on sex-differences have demonstrated that the relationship between uric acid and CV stiffness observed in the general population is largely driven by the effect in women. These relationships are shown in **figure 1**, where quartiles of serum uric acid (x-axis), are presented for men and women and reveal that the level of arterial stiffness increases with increasing uric acid concentrations only in women (**fig. 1A and 1B**), as does the prevalence of diastolic dysfunction (a composite measure of cardiac stiffness) shown in **figure 1D**.

**Negative metabolic effects of dietary fructose** - The PI of the present project was an organizer of an NIH consensus conference on the potential negative metabolic effects of dietary fructose (2). The consensus panel called for research to test hypotheses related to whether a reduced-sugar intervention that causes weight loss would improve disease biomarkers for CV risk. With respect to known fructose effects on the metabolic syndrome, supplementation of dietary fructose increases body weight, plasma triacylglycerols (TG), lowers HDLc (3), and raises ambulatory blood pressure (4) and the latter effect can be blocked by the xanthine oxidase inhibitor, allopurinol (5). In rodents, fructose feeding to induce the metabolic syndrome is mediated partly by hyperuricemia but doses needed for this effect can be high, due to rats having the enzyme uricase, which hydrolyzes uric acid. By contrast, humans do not

## PROTOCOL: Project

Project Title: "A short term evaluation of a structured weight loss plan in overweight and obese adults"  
 Version 1 Date: March 18, 2016

produce this enzyme and graded doses of fructose in the diet incrementally increase uric acid concentrations (3). Stanhope et al found a linear relationship between fructose supplementation (from 0%, to 10%, 17.5%, and 25% of energy) and increasing serum uric acid, which was higher by 11% at the top dose ( $P<0.0001$  for effect of dose). In line with the expert consensus, the design of human studies should allow for better translation of the large amount of preclinical (rodent) data on the detrimental CV effects of fructose feeding in rodents and do so, in humans, by practical dietary means. Lastly, the consensus highlighted one scientific area in critical need of further research – investigation of the effects of dietary sugar intake in at-risk populations, i.e., those already consuming diets high in added sugars.

**Figure 1.** Relationships between serum uric acid and CV stiffness between the sexes

[figure not shown]

Fig. 1A and 1B modified from Fang et al. The comparison of brachial-ankle pulse wave velocity level among subjects with different quartiles of serum uric acid (sUA) concentrations by gender, based on ANCOVA (adj for age, obesity, SBP, fasting glucose, hypercholesterolemia, hypertriglyceridemia, low HDL-C, smoking habit, alcohol consumption and vigorous exercise).  $P$ -values compare the pulse wave velocity values at quartiles 2, 3 and 4 with quartile 1.

Fig. 1C and 1D modified from Nogi et al. The association between serum UA concentration quartiles and diastolic dysfunction by logistic regression (adj for age, Log(eGFR), SBP, pulse rate, diuretics, both loop or thiazide).  $P$ -values compare the prevalence of diastolic dysfunction at quartiles 2, 3 and 4 with quartile 1.

As described Stanhope (3), an increased intake of added sugars in the diet is associated with dyslipidemia, CVD, and metabolic syndrome (6, 7) and, as shown in **table 1**, data from the NHANES suggest that the higher the intake of added sugars, the greater the CVD risk (8). The average dietary amount of added sugars in U.S. adults 20–60 years is 13–14% of daily calories and, importantly, is significantly associated with an 18% increase in CVD mortality risk. Posthoc analysis of data from the PI's most recent weight-loss study in subjects with metabolic syndrome agree with this analysis.

**Table 1.** NHANES data on intake of added sugars

Quintile of added sugars in the diet	Adjusted hazard ratio of CVD mortality
Q1 0 - 9.6%	1.00 referent
Q2 9.6 - 13.1%	1.07 (1.02-1.12)
Q3 13.1 - 16.7%	1.18 (1.06-1.31)
Q4 16.7 - 21.3%	1.38 (1.11-1.70)
Q5 ≥ 21.3%	2.03 (1.26-3.27)

[figure not shown]
$n = 11,733$ . Added sugars represented as the energy from sugars relative to total dietary energy (kcal/kcal). HR (95% confident interval),  $P = 0.004$  for dose.

As shown in **figure 2**, ad libitum diets in men contained  $9.3 \pm 3.6\%$  of energy as added sugars, which was significantly lower than the baseline intake in women ( $16.6 \pm 8.1\%$ ,  $P<0.02$ ).

## PROTOCOL: Project

Project Title: "A short term evaluation of a structured weight loss plan in overweight and obese adults"  
 Version 1 Date: March 18, 2016

**Figure 2.** Sex specific changes following fructose-restriction

Data are mean  $\pm$  SE. Men (n=7) and women (n=9) participated in a program of energy restriction targeted at reducing consumption of added sugars.

These subjects participated in a program designed to reduce dietary sugar intake and body weight. Weight loss was similar in men ( $-10 \pm 3\%$ ) and women ( $-10 \pm 2\%$ ,  $P=0.99$ , data not shown) but women reduced their sugar intake more than men (fig. 2A). Further, in women, limiting dietary sugars and body weight loss significantly reduced both systolic (fig. 2B) and diastolic blood pressure (fig. 2C). Even in this relatively small sample size, serum uric acid in women tended to be reduced with weight loss while it was unchanged in men (fig. 2D) exhibiting a significant time by sex interaction ( $P=0.006$  by ANOVA). Overall, these data demonstrate that the higher added sugar intake of women is a modifiable characteristic that can improve blood pressure and serum uric acid. Our proposed study expands the use of these established procedures by adding a state-of-the-art measure of arterial stiffness - pulse wave velocity (PWV).

The present study is designed to cause weight loss acutely through consumption of a diet that is restricted in calorie and simple sugars. Both men and women will be studied and their results compared to determine whether women benefit more with respect to arterial stiffness. Upon finishing the four-week diet intervention, body weight and blood lipids will be assessed to compare the longer term effect on blood pressure.

## PROTOCOL: Project

Project Title: "A short term evaluation of a structured weight loss plan in overweight and obese adults"

Version 1 Date: March 18, 2016

**Summary of Study Objectives**

We will accomplish the following specific aims:

**Aim 1 (weight loss):** To induce weight loss, overweight/obese subjects will be fed with a 2-week calorie-restricted diet. This specially formulated diet (see Appendix) will be low in carbohydrates. After this two weeks, the subjects will prepare their own food based on the Atkins online diet program for subsequent 2 weeks. ***Hypothesis 1:*** *After four weeks of a calorie-restricted diet feeding, the subjects will lose 3-6% of their body weight.*

**Aim 2 (arterial stiffness improvement):** To quantify arterial stiffness improvement by measuring aortic pulse-wave velocity (PWV). ***Hypothesis 2:*** *After four weeks of feeding, the subjects will have lower serum uric acid level and lower aortic PWV. Further, the female participants will have even more improvement of PWV compared to men.*

**AIM 3 (lifestyle impact on body weight):** To assess the impact of individual lifestyle factor on the change of body weight, blood pressure and heart rate. ***Hypothesis 2:*** *During the four weeks of follow-up, the changes of subjects' body weight, blood pressure and heart rate will reflect their lifestyle.*

**Impact:** The present study to evaluate the effect of a calorically-restricted diet on body weight and arterial stiffness in overweight and obese adults. The data generated by this study will determine whether arterial stiffness can be improved by short-term low carbohydrate diet, and the potential mechanism by which uric acid level impacts CV risk in overweight and obese adults, especially in women. This study will also provide the important preliminary data for an NIH R01 grant submission.

**Study Design**

The sources of research material will be subject and family medical history, physical exam, screening laboratory tests, Dual-energy X-ray absorptiometry (DEXA, total and regional fat mass and fat-free mass), blood tests, aortic PWV, indirect calorimetry data and behavior questionnaires. Demographic data (plus other related data: emergency contact person, pregnancy status), blood pressure and morphometrics will be measured (height, weight). Lifestyle information including food intake and physical activity will be obtained. Each subject will donate 280 ml of whole blood for all combined blood draws performed for the screening and baseline test and the rest four interim and follow-up tests.

**Table 2** shows how the 280 ml of blood given by the subject is allotted over the course of the study.

The participant will consume two weeks of either a "Jump Start" or a "Grab-and-go" diet after the baseline visit 1 (please refer to the Appendix for meal composition and calorie density).

**Table 2. Accounting of Blood Usage**

Procedure	Volume of whole blood (mls)
Screening blood chemistries	40
Baseline visit 1	60
Interim visit 2	30
Follow-up visit 3	60
Follow-up visit 4	30
Final visit 5	60
Total for each subject (mls)	280

## PROTOCOL: Project

Project Title: "A short term evaluation of a structured weight loss plan in overweight and obese adults"

[figure not shown]
Version 1 Date: March 18, 2016

**Overall activities**

The study tests will be completed through a total of 6 visits (and 3 food pick ups). Please see the study timeline below. First, screening laboratory tests are used to assess general medical status. Second, during the baseline visit 1, the subject's aortic PWV is measured to assess the arterial stiffness.

Fasting blood is collected to measure the baseline serum uric acid, creatinine, insulin, glucose and lipid level. A fasting urine sample is collected to measure urinary ketones. Third, the subject's body weight, waist, blood pressure, heart rate and fasting urinary ketone will be determined during the interim visit 2. Fourth, the tests performed at the baseline visit will be repeated during the follow-up visit 3. Blood collected during the baseline and final visits is processed to obtain plasma or serum, and the entire sample is used in the isolation and measurement of blood metabolites and hormones including glucose, TG, FFA, liver function tests, insulin, and plasma hormones. Physical activity before participation in the study and during the 4-week of diet consumption will be monitored by wearing an accelerometer device.

Study Timeline: times of blood draws denoted with an \*

Upon finishing the dietary intervention, the subjects come back for follow-up visit 4 at week 6 and final visit 5 at the end of week 8 to measure blood pressure, heart rate and body weight. The subjects will be asked to fill out questionnaires to assess the behavior and lifestyle change. Once the data acquired, the processed samples will be kept until at least 10 years after publication. The sample tubes are labeled with the subject's study number. No identifying information is present on the tubes. No tools (e.g., cell lines, probes, etc) will be generated from any of this material. All samples are coded to conceal the subjects' identities.

**Subject Compensation**

For screening visit, subjects receive no compensation, \$25 for completing the baseline test, \$75 for consuming a 2-week specially formulated diet, and \$100 for finishing the follow-up test 3 and \$25 each for returning for visits 4 and 5 (\$250 total).

**Study design and data analysis**

Our statistical analysis plan, designed in consult with [name], is based both on our preliminary data (**fig. 2**) and data from the increased body of literature that has been generated over the past few years (9-12). The present study is designed to generate data from a future grant and thus, we will use the data generated here for future sample size estimation. For analysis, study group characteristics will be summarized with descriptive statistics and the data will be analyzed as % and absolute change.

Paired t-tests will be used to test if the within-group changes are significantly different from zero, and a one-way analysis of variance applied to the "change scores" will be used to test for group (sex)

## PROTOCOL: Project

Project Title: "A short term evaluation of a structured weight loss plan in overweight and obese adults"

Version 1 Date: March 18, 2016

differences with respect to change. If the overall ANOVA test is significant, pairwise comparisons will be carried out to determine which groups differ. A technique such as the Bonferroni-Holms procedure will be used to correct for multiple testing. Standard ANOVA methods rest on the twin assumptions of normally distributed errors and equal variances across groups. Depending on the distribution of the individual variables, Pearson or Spearman correlation coefficients will be used to examine pairwise associations between continuous variables. Results will be reported as sex group means or medians, as are most appropriate for the data, along with 95% confidence intervals for the summary statistics. Statistical analysis will be performed with SAS software (SAS Institute, Cary, NC).

**Table 3** below shows the major outcomes measured in this study and the anticipated results at the end of 4-week dietary intervention.

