**Table 3. Study outcomes and anticipated results at the end of 4-week dietary intervention**

Primary outcome variable	Method of detection	Baseline to Visit 3 change
Body weight	Weight scale	↓
Waist circumference	Tape measure	↓
Body fat percentage	DEXA	↓
Blood pressure	Blood pressure cuff	↓
Energy expenditure	Indirect calorimetry	↓
Lipid level	Enzymatic assay	↓
Glucose and insulin level	Enzymatic assay and ELISA	↓
Fructose level	Enzymatic assay	↓
Uric acid level	ELISA	↓
Creatinine level	ELISA	↓
Urinary ketone level	Enzymatic assay	↓
Carotid-femoral PWV	SphygmoCor XCEL device	??

Abbreviations: DEXA, dual-energy X-ray absorptiometry; Indir. cal., indirect calorimetry; ELISA, enzyme-linked immunosorbent assay; PWV, pulse wave velocity

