### Schedule of Events

#### *Screening*

Twenty overweight/obese subjects (10 men and 10 women, 30-55 yrs old) will each participate in the 4-week dietary intervention and 4-week follow-up phase. Eligibility is determined through interactions between study staff and the subjects (initial phone conversation and a screening visit). During the screening visit at the clinical research center (CRC), after signing the consent form, the subject undergoes a fasting blood draw (40 ml) to rule out the presence of diabetes and blood is drawn for serum HbA1c, complete blood count, thyroid, liver (liver enzymes and hepatitis), and kidney function, and a lipid panel are measured. Medical information is obtained including DOB, gender, ethnic/racial category, height, body weight (history of body weight) and medical history (medication use, smoking history). The subject is fed breakfast after blood draw and fills out surveys to assess physical activity, typical food intake, food cravings and sleep quality.

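### Planned correlations carry no sex term, so a uric acid–PWV correlation pooled over men and women could reflect the sex difference alone; prespecify sex-adjusted and sex-specific estimates

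*Combined protocol and SAP*

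**What the plan says.** The protocol's section on study design and data analysis gives one method for relating two continuous variables: "Pearson or Spearman correlation coefficients will be used to examine pairwise associations between continuous variables", with the choice depending on distribution. It names no covariate and no pair of variables. It does not say whether levels or changes are correlated, or whether the sexes are pooled. Sex enters the plan through the one-way ANOVA of change scores and through reporting of means or medians by sex.

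The sample is "Twenty overweight/obese subjects (10 men and 10 women, 30-55 yrs old" at enrolment. Two places lead one to expect a sex difference in both variables:

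- **Uric acid.** The pilot data under Figure 2 are described as "exhibiting a significant time by sex interaction" (P=0.006), from 7 men and 9 women.
- **PWV.** Hypothesis 2, under Aim 2, predicts that "the female participants will have even more improvement of PWV compared to men". No size is given, and Table 3 shows question marks for the expected PWV change.

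The Impact paragraph says the data will address "the potential mechanism by which uric acid level impacts CV risk in overweight and obese adults, especially in women".

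**The concern.** When two variables both shift with sex, they are correlated across the combined sample even if they are unrelated among men and among women. A uric acid–PWV coefficient from all 20 subjects would then partly restate the sex difference that Hypothesis 2 already tests by ANOVA.

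The paired t-tests and the ANOVA cannot link one outcome to another, so any statement about uric acid as a mechanism would have to draw on the correlation sentence. The study is meant to supply preliminary data for a grant application and for future sample size estimates. A coefficient produced by sex alone could be carried into both.

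**Working it through.** The plan states no power, alpha or effect size for correlations, so there is no figure of its own to reproduce. The check asks how often a pooled correlation would be significant when there is no association within either sex.

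**Inputs**

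- 10 men and 10 women (Screening section).
- Pilot sex difference in uric acid change: P=0.006, with 7 men and 9 women (Background, Figure 2).
- Sex difference in PWV change: direction only (Hypothesis 2). Assumed range 0 to 1.63 SD.
- Alpha: not stated. Assumed two-sided 0.05.

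**Step 1: uric acid effect from the pilot P value.** With 7 + 9 − 2 = 14 degrees of freedom, two-sided P=0.006 gives t = 3.23. Then d = t × √(1/7 + 1/9) = 3.23 × 0.504 = 1.63.

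**Step 2: correlation created by sex alone.** With equal groups, unit within-sex SDs and zero within-sex correlation,

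r = (d₁d₂/4) / √[(1 + d₁²/4)(1 + d₂²/4)].

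With d₁ = 1.63, this gives r = 0.15 for d₂ = 0.5, 0.28 for d₂ = 1.0 and 0.40 for d₂ = 1.63.

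**Step 3: rejection rates.** Simulation with 100,000 replicates per scenario, normal change scores, zero within-sex correlation:

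| Uric acid d | PWV d | Pooled Pearson | Pooled Spearman | Sex-adjusted Pearson |
|---|---|---|---|---|
| 1.63 | 0 | 5.1% | 5.2% | 5.0% |
| 1.63 | 0.2 | 6.0% | 5.9% | 5.1% |
| 1.63 | 0.5 | 10.1% | 10.3% | 5.1% |
| 1.63 | 1.0 | 23.6% | 24.6% | 5.1% |
| 1.63 | 1.63 | 45.8% | 48.5% | 5.0% |
| 1.0 | 1.0 | 13.6% | 13.9% | 5.0% |

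Spearman, the plan's alternative, gives no protection.

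**Step 4: a smaller uric acid effect.** The same pilot paragraph describes only a tendency to fall in women and no change in men. Suppose that tendency means P between 0.05 and 0.10 with n = 9 (an assumption). Then t on 8 degrees of freedom is 1.86 to 2.31, and dividing by √9 gives 0.62 to 0.77 SD. With men at zero and equal SDs, that is also the sex difference. Pooled rejection is then about 6% to 7% at a PWV d of 0.5, and about 9% to 10% at 1.0.

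**Step 5: what the PWV values would mean.** The baseline visit section gives a test-retest SD of 8%. Taking this as a floor for the SD of PWV change, d = 0.5 needs a sex difference of at least 0.5 × 8 = 4 percentage points (about 0.25 m/s at 6.13 m/s). A d of 1.63 needs at least 1.63 × 8 = 13 points (about 0.80 m/s) within four weeks.

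**Step 6: what adjustment can and cannot do.** If the true correlation is 0.5 in both sexes, the sex-adjusted test has about 62% power. If it is 0.5 in women and 0 in men, the adjusted coefficient averages about 0.24 and is significant only about 19% of the time.

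**The case against.** **The text does not say pooled.** A reader might infer that the plan ignores sex in its correlations. The documents do not support that: the neighbouring sentences are organised by sex, and within-sex correlations would fit the wording. This stands. The gap is that the choice is left open and could be made after the data are seen.

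**The pair is not named.** Hypothesis 2 concerns a fall in each variable and a sex difference in PWV, and the ANOVA covers the latter. No uric acid–PWV correlation is prespecified, and no primary conclusion depends on one. This also stands, and it limits the weight of the point. The Impact paragraph's interest in mechanism still has no other planned analysis behind it.

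**The larger rates rest on assumed effects.** A reader might infer a false-positive rate of 10% to 46% as a property of the plan. It is not. The PWV effect is assumed, and with little or no PWV sex difference the rate is 5% to 6%. The top figure transfers the uric acid effect to PWV. The 1.63 SD comes from a significant result in 16 people and sits poorly with the pilot's wording, although a rise in men or unequal SDs could reconcile the two. Nor is false positive the right term: in these scenarios the pooled correlation truly is non-zero, and the error lies in reading it as a link within individuals of either sex.

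**Partial correlation alone suits the hypothesis poorly.** It summarises one common association, whereas the Background reports that stiffness rises with uric acid in women only. Step 6 shows the loss. This stands and changes the remedy: sex-specific estimates need equal standing.

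**Conclusion.** The point holds as a cheap improvement. The plan specifies no sex adjustment for its correlations although it expects both uric acid and PWV to change more in women. Pooling would then confound the association with sex.

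The size is conditional. With a uric acid difference of 1.63 SD and a PWV difference anywhere from 0 to 1.63 SD, a pooled test is significant in about 5% to 46% of trials without any within-sex association. With about 0.6 to 0.8 SD for uric acid and 0.5 to 1.0 SD for PWV, it is about 6% to 10%. These figures assume normal change scores, equal within-sex SDs, 10 subjects per sex and two-sided 5% tests. Sex adjustment holds the rate at about 5% in every scenario. That adjustment is worthwhile does not depend on which scenario is nearest the truth.

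**What to change.** In the data analysis section, replace the correlation sentence with text to this effect: associations between change scores are estimated by Pearson or Spearman partial correlation controlling for sex; sex-specific coefficients with 95% confidence intervals are reported as co-equal results, because the link is hypothesised to be stronger in women; unadjusted pooled coefficients are descriptive only.

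The data are already collected, and in SAS the adjustment is one PARTIAL statement. The cost is one degree of freedom (17 instead of 18) and a plain admission of imprecision. With 10 subjects in a sex, an observed r of 0.5 has a Fisher-z interval of 0.549 ± 1.96/√7 = 0.549 ± 0.741 on the z scale, which is about −0.19 to 0.86. The sex-specific results should therefore be presented as estimates for planning, not as tests.
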